2.5 Identification and description of the investigational medication or medications

The ACORES-2 trial does not involve the use of an experimental medication (usual RAS blockers).

All the patients included in the ACORES-2 trial are already taking RAS blockers before participating in the research.

The experimental arm is therefore the discontinuation of this therapy.

2.6 Description and justification of the dosage, route of administration, administration schedule and treatment duration

The dosage will be the usual patient's one. In the continuation group, the treatment will be continued

RAS blockers are given according to the standard of care and the choice of the prescribed RAS blocker (INN and dosage) are unrelated to their participation in the research.

- For all patients randomized in the discontinuation group, an alternative treatment will be proposed according to the appropriate guidelines of the European Society of Cardiology (hypertension, heart failure, coronary artery disease) and the tolerance of the patient

In particular :

- in individuals at risk of uncontrolled blood pressure: consider Calcium Channel blocker as a first line option, if necessary other antihypertensive drug (non-RAS blockers) can be added according to the physician decision
- In individuals with history of heart failure: consider adding diuretics and nitrates (oral or IV according to the physician decision)

2.7 Summary of the known and foreseeable benefits and risks for the research participants

The potentials benefits of discontinuation of RAS blockers for the participants are the following:

- Reduction of the risk of developing severe forms of COVID-19 by reducing the synthesis of ACE2 and the infection of patient's cells by the SARS-CoV-2
- Reduce the delay to recovery and hospital discharge
- Reduction of hypotension requiring vasopressors
- Reduction of the rate of acute kidney injury
- Better knowledge of the impact of RAS blockers on the acute lung injury related to coronaviruses.
- Better knowledge of the impact of RAS blockers withdrawal in cardiovascular high-risk patients

The potentials risk of discontinuation of RAS blockers for the participants are the following:

- Increase of cardiovascular events, such as acute heart failure, uncontrolled hypertension, myocardial infarction or stroke
- Increase of COVID-19 related acute lung injuries by reducing the synthesis of ACE2 and angiotensin(1-7)

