4.2.4 Randomization

Randomization will be performed with IWRS (Cleanweb).

[figure not shown]
URC Lariboisière Saint-Louis will be done randomization list according to AP-HP Standard Operating Procedures (SOP).

Patients fulfilling the inclusion criteria and without any exclusion criteria that agree to enter the protocol and have signed the inform consent form during the consultation (inclusion) will be randomized in a 1:1 ratio to:

- Group Discontinuation = discontinuation of RAS blocker therapy until the end of the study which correspond to day 28 (experimental arm). After day 28, RAS blockers could be reintroduced or not, according to the physician decision.
or
- Group Continuation = continuation of RAS blocker therapy (control arm)

The randomization will be stratified on the indication of RAS blockers (heart failure vs. other indication).

Inclusion and randomization will be done the same day.

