- Symptoms compatible with SARS-CoV-2 infection: fever, cough, dyspnea, anosmia, ageusia, ocular congestion, myalgia, sputum production, anorexia, fatigue, headache, sore throat, rhinorrhea, digestive symptoms (diarrhea, nausea, vomiting)
- Complete physical examination
- Biology: complete blood count, creatinine, blood urea nitrogen, potassium, sodium, bicarbonate, alanine/aspartate aminotransferase, bilirubin, albumin, lactate dehydrogenase, prothrombin time, activated partial thromboplastin time, D-dimers, troponin I us, creatine kinase, natriuretic peptides (BNP or Nt-proBNP), C-reactive protein, procalcitonin, ferritin, arterial blood gas with lactate
- Blood group and rhesus will be determined at inclusion if not performed earlier. Data will be collected in the CRF. Indeed, it has been reported in 2,173 Chinese patients with COVID-19 that blood group A was associated with a higher risk for acquiring COVID-19 compared with non-A blood groups, whereas blood group O was associated with a lower risk for the infection compared with non-O blood groups. this observation was reported in a preprint article without peer-review and further investigation are of the relationship between the ABO blood group and the COVID-19

susceptibility is important (Zhao J, Yang Y, Huang H, Li D, Gu D, Lu X, et al. Relationship between the ABO Blood Group and the COVID-19 Susceptibility. medRxiv. 27 mars 2020;2020.03.11.20031096.)

Any arterial puncture for collecting arterial blood gas and/or lactate should be performed after topical anesthesia with lidocaine 5% cream (EMLA)™

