5.2 Every day visit in hospitalization until day 28, discharge or death

The patients will have a daily visit during hospitalization until day 28, discharge or death. All the events occurring during hospitalization will be collected prospectively, as well as the date of onset:

- Clinical status on a seven-category ordinary scale (as defined above) each day
- Hospital discharge
- Cross-over
- Cardiovascular death
- Non cardiovascular death and cause
- myocardial infarction
- Myocarditis
- Stroke
- Heart failure; presence of congestive signs, IV use of diuretics
- Acute kidney injury, as defined in the KDIGO (Kidney Disease: Improving Global Outcomes) guidelines (45): increase in serum creatinine $\geq 26.5 \mu\text{mol/L}$ within 48h or ≥ 1.5 times baseline within the last 7 days or urine output $< 0,5 \text{ ml/kg/h}$ for 6 hours
- ICU admission (and date of discharge if happens)
- Oxygen requirement: date of beginning and cessation
- Mechanical ventilation (non-invasive or invasive): date of beginning and cessation
- Acute respiratory distress syndrome, as define by the Berlin criteria (46): acute lung injury ≤ 1 week, bilateral opacities consistent on chest imaging not fully explained by other lung pathology, heart failure or volume overload, $\text{PaO}_2/\text{FiO}_2$ ratio $\leq 300\text{mmHg}$ with a minimum of 5 cm H_2O PEEP (or CPAP)
- Shock requiring vasopressors
- Extracorporeal membrane oxygenation (ECMO): date of beginning and cessation
- Renal replacement therapy: date of beginning and cessation
- Biology: as mentioned at 5.1, according to the physician's decision

5.3 End of study visit (visit or phone call at day 28 \pm 4 days)

- All patients still hospitalized at day 28, will have a visit with an events collection as mentioned at 5.2.
- All survivors' patients already discharged from hospital will have a phone call by an investigator (physician) at day 28 (± 4 days) to collect the events occurred since discharge from hospital:
 - Clinical status on a seven-category ordinary scale (as defined above)
 - New hospitalization in a non-ICU
 - Cardiovascular death

- Non cardiovascular death and cause
- Myocardial infarction
- Myocarditis
- Stroke
- Heart failure; presence of congestive signs, IV use of diuretics
- Acute kidney injury, as defined in the KDIGO guidelines
- ICU admission
- Oxygen requirement: date of beginning and cessation
- Mechanical ventilation (non-invasive or invasive): date of beginning and cessation

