8.1.6 Acute kidney injury

Acute kidney injury is defined by the KDIGO Guidelines as follows (45):

- increase in serum creatinine $\geq 26.5 \mu\text{mol/L}$ within 48h
- or increase in serum creatinine ≥ 1.5 times baseline within the last 7 days
- or urine output $< 0,5 \text{ ml/kg/h}$ for 6 hours

Its severity is staged according to the following criteria:

- stage 1:
 - increase in serum creatinine $\geq 26.5 \mu\text{mol/L}$ within 48h
 - or increase in serum creatinine ≥ 1.5 times baseline within the last 7 days
 - or urine output $< 0.5 \text{ ml/kg/h}$ for 6 hours
- stage 2:
 - increase in serum creatinine 2-2.9 times baseline
 - or urine output $< 0.5 \text{ ml/kg/h}$ for ≥ 12 hours
- stage 3:
 - increase in serum creatinine $\geq 353.6 \mu\text{mol/L}$
 - or increase in serum creatinine ≥ 3 times baseline
 - or initiation of renal replacement therapy
 - or urine output $< 0.3 \text{ ml/kg/h}$ for ≥ 24 hours
 - or anuria ≥ 12 hours

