12.4.2 Secondary Efficacy Criteria

If a significant difference is found for the main criterion, The secondary criteria will be tested using a hierarchical procedure in the following order:

1. Clinical status as assessed with the seven-category ordinal scale on days 28.
3. Number of days alive free of oxygen.
4. Number of days alive outside hospital during 28 days after randomization.
5. Number of days alive free of intensive-care unit (ICU) admission or mechanical ventilation (invasive or non-invasive) 28 days after randomization.
6. Number of days alive free of mechanical ventilation (invasive or non-invasive) 28 days after randomization.
7. Number of days alive free of ICU admission 28 days after randomization.
8. Rate of all-cause mortality at day 28.
9. Rate of cardiovascular death at day 28.
10. Number of days alive free of acute kidney injury during hospitalization.

Secondary criteria will be compared using Mann-Whitney tests for quantitative variables and ordinal logistic regression to analyze the seven-category ordinal. Chi-square tests for categorical data and Cox survival analysis for time to event. Tests will be performed at a two-sided 5% significant level for one criterion only if a significant difference has been found for the previous criterion in the list.

Differences in medians between groups will be reported with associated 95% CI

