14 ETHICAL AND LEGAL CONSIDERATIONS

14.1 Methods for informing research participants and obtaining their consent

- **Who is informed?** *The participant*
- **Who is providing consent?** *The participant*
- **When?** *At Baseline*
- **How?** *Information note given to the participant and oral explanation*
- **Who informs and obtains the consent?** *The investigator, or a physician representing the investigator*

In accordance with Article L1122-1-1 of the Code de la Santé Publique (French Public Health Code), no interventional research involving human participants can be carried out on a person without his/her freely given and informed consent, obtained in writing after the person has been given the information specified in Article L.1122-1 of the aforementioned Code.

A reflection period of **6 hours** is given to the individual between the time when he or she is informed and when he or she signs the consent form.

The person's freely given, written, informed consent will be obtained by the principal investigator or a physician representing the investigator before the person is enrolled in the study at Baseline (max 7 days after hospitalization).

A copy of the information notes and consent form signed and dated by the research participant and by the principal investigator or the physician representing the investigator will be given to the individual prior to their participation in the study. The principal investigator or the physician representing him/her will keep a copy.

At the end of the study, one copy will be placed in a tamper-proof sealed envelope containing all the consent forms. This envelope will be archived by the sponsor.

In addition, the investigator will specify in the person's medical file the person's participation in the research, the procedures for obtaining his/her consent as well as the methods used for providing information for the purpose of collecting it. The investigator will retain one copy of the signed and dated consent form.

14.2 Prohibition from participating in another clinical study or exclusion period set after the study

Participants include in this study cannot be enrolled in any another interventional research protocol until completing the last visit of the ACORES 2 trial (day 28)".

Participants can participate to any observational study.

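### AKI already present at randomisation can count towards the AKI outcome in both arms, and the planned unadjusted test ignores it: a modest, avoidable loss of precision, not a bias

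*Protocol*

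**What the plan says.** - **Definition.** Section 8.1.6, repeated in the daily-visit list of 5.2, calls AKI any one of three things: a creatinine rise of at least 26.5 µmol/L within 48 h, a rise to at least "1.5 times baseline within the last 7 days", or low urine output over 6 hours. Neither place dates the baseline value or asks that the criterion be first met after randomisation.
- **Timing of entry.** Under 14.1 a patient is to consent before being "enrolled in the study at Baseline (max 7 days after hospitalization"), and 4.2.4 adds: "Inclusion and randomization will be done the same day". Day 0 can therefore fall as late as a week into the stay.
- **Eligibility.** The only renal exclusion in 6.2 is a history of nephrotic syndrome.
- **Data.** Section 5.1 takes creatinine at day 0 ("Biology: complete blood count, creatinine, blood urea nitrogen"). Section 5.2 states: "All the events occurring during hospitalization will be collected prospectively, as well as the date of onset". Section 5.1 records chronic renal insufficiency but not AKI status at day 0.
- **Endpoint and test.** AKI-free days are counted over the hospitalisation. Most of the other day counts are tied to the 28 days after randomisation; this one is not. It is the last of nine endpoints in the hierarchy of 12.4.2, where "Secondary criteria will be compared using Mann-Whitney tests for quantitative variables". Section 12.5 gives dichotomised safety endpoints a chi-square test.
- **Motive.** Section 2.7 lists among the expected benefits: "Reduction of the rate of acute kidney injury".

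**The concern.** A patient who is already in AKI when randomised can meet the definition on the first study day in either arm. The strategy cannot have caused or prevented the onset of that episode, though it may change how long it lasts. Two things follow. In a comparison of AKI rates, the same block of pre-existing cases is added to both arms and the contrast shrinks. In AKI-free days, day-0 AKI is a strong predictor of the outcome, and a Mann-Whitney test that ignores it leaves that variation in the comparison. At stake is power on a question the protocol names as part of its rationale (2.3) and as an expected benefit (2.7).

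**Working it through.** **The plan's own figure.** None exists to reproduce. The 277 per arm in section 12.8 is sized for time to clinical improvement; no power is given for AKI.

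**Inputs from the protocol.** 277 per arm (12.8); 28-day mortality 22% (10.3.2.2, in the part on events not needing immediate notification); AKI 3-15% in published cohorts, listed among causes of ICU admission (2.2).

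**Assumed.** New AKI among patients free of it at day 0: 10% (continuation) versus 4% (discontinuation). Share q already in AKI at day 0: 3%, 5.6% or 10%. The middle value is the largest q that keeps total control-arm AKI at 15%: q + (1 − q) × 0.10 = 0.15 gives q = 0.05/0.90 = 5.6%.

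**Step 1: any AKI, yes or no.** With prevalent cases counted, p_c = q + (1 − q) × 0.10 and p_d = q + (1 − q) × 0.04, so the difference is (1 − q) × 0.06. With p̄ the mean of the two,

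z = [ |p_c − p_d| × √277 − 1.96 × √(2 p̄(1 − p̄)) ] / √( p_c(1 − p_c) + p_d(1 − p_d) ), power = Φ(z).

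- q = 0: 0.10 versus 0.04; z = (0.999 − 0.707)/0.358 = 0.81; power 79%.
- q = 10%: 0.190 versus 0.136; z = (0.899 − 1.024)/0.521 = −0.24; power 41%.
- q = 3%: 64%. q = 5.6%: 53%.

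Counting only new AKI, among the 277 × (1 − q) patients per arm free of it at day 0, gives 78%, 77% and 75% at q = 3%, 5.6% and 10%.

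**Step 2: AKI-free days, the listed endpoint.** Simulation with 3,000 trials per cell (Monte Carlo standard error at most 0.9 points). Further assumptions: 28-day count from randomisation; AKI duration gamma (shape 2, mean 7 days); onset of new AKI uniform over days 0-14; deaths equal in both arms, unrelated to AKI and scored 0 days. Each cell shows power for plain Mann-Whitney, then for van Elteren stratified on day-0 AKI.

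| Mortality | q = 3% | q = 5.6% | q = 10% |
|---|---|---|---|
| 0% | 66%, 76% | 52%, 65% | 41%, 57% |
| 10% | 29%, 31% | 25%, 29% | 22%, 25% |
| 22% | 15%, 15% | 14%, 14% | 12%, 13% |

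If discontinuation also shortens existing AKI by 30%, the pairs at q = 5.6% become 55%, 85% (no deaths), 28%, 42% (10%) and 15%, 21% (22%).

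**Step 3: validity.** With new AKI at 10% in both arms and q = 10%, rejection rates were 4.9% (Mann-Whitney) and 5.5% (van Elteren) without deaths, and 5.0% and 4.8% at 22% mortality.

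**The case against.** **A reader might infer that AKI present at day 0 counts against one strategy.** The documents do not support that. Allocation is randomised 1:1, so these cases are balanced in expectation, and step 3 shows the plain test keeps its level. The planned test is valid; the issue is efficiency.

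**A reader might also take 3-15% as the day-0 prevalence and conclude that power collapses.** Section 2.2 gives that range among causes of ICU admission, whereas section 5.1 recruits in non-ICU departments and 6.2 excludes shock on vasoactive drugs and ventilated ARDS. With 10% new AKI on top, q = 10% already puts total control-arm AKI at 19%, above the top of that range. The steep fall in step 1 also belongs to an any-AKI comparison, which is not in the hierarchy and could arise only under the general line in 12.5.

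**Mortality matters more.** At the protocol's 22%, AKI-free days have little power whichever test is used. The endpoint is also tested only if the primary and all eight earlier secondaries are significant. Both points stand, and they limit the practical effect.

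**Baseline may mean the day-0 visit,** which the schedule in 5.5 labels that way. The 1.5-fold criterion would then need a rise from day 0, and only the 48 h and urine criteria could reach back. But a creatinine already raised at day 0 would become the reference and hide existing AKI. The text allows both readings.

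**The 7 days is a maximum,** and the consent table in 5.1 places information at hospital admission with a 6-hour reflection period. Exclusion 8 (RAS blocker stopped for more than 48 h) may also remove some early AKI. Both could make q small.

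**These are details for the analysis plan, and onset dates are already collected.** This stands in part: a plan not shown may date the baseline value and derive day-0 status. The protocol itself, however, fixes both the definition and the unadjusted test.

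**Conclusion.** The point holds as a precision issue. As written, the definition lets AKI present at day 0 be counted in both arms, and the test named for AKI-free days makes no allowance for it. There is no bias and no inflation of type I error.

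The size rests on assumptions, because the protocol gives neither a day-0 prevalence nor an expected AKI effect. Over 3-10% prevalence with new AKI 10% versus 4%, stratification recovers about 10-16 points of power with no deaths, 2-4 points at 10% mortality and almost nothing at 22%. It recovers more if discontinuation also shortens existing AKI. Scoring deaths as 0 days is also an assumption. Given the endpoint's last place in the hierarchy, this is an optional improvement and no threat to the trial's main conclusions.

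**What to change.** 1. In 8.1.6 and 5.2, state which creatinine value is the baseline for the 1.5-fold criterion.
2. Flag AKI present at day 0, using the creatinine already taken under 5.1.
3. In any comparison of AKI rates, count only AKI whose criteria are newly met after randomisation.
4. Keep every randomised patient in AKI-free days, counted from randomisation. Replace the plain Mann-Whitney test with a van Elteren test stratified on day-0 AKI, or a rank or ordinal model adjusted for day-0 AKI or creatinine.

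The cost is one case-report-form flag and a few sentences on definition and analysis. It needs no extra patients or samples and no change in care. Keeping all patients in item 4 preserves the intention-to-treat comparison.

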8.1.7 Acute respiratory distress syndrome (ARDS)

ARDS is defined by the Berlin definition (46) as the association of the following criteria:

- acute lung injury ≤ 1 week of a known clinical insult or new worsening respiratory symptoms
- chest imaging (X-ray or CT) showing bilateral opacities not fully explained by effusions, lobar/lung collapse or nodules

- respiratory failure not fully explained by cardiac failure or fluid overload
- $\text{PaO}_2/\text{FiO}_2$ ratio ≤ 300 mmHg with a minimum of 5 cm H₂O PEEP (or CPAP)

8.1.8 Shock requiring vasopressors

A. Cardiogenic shock

Cardiogenic shock is defined as follow, based on the basis of the and the CULPRIT-SHOCK Study (51,52).

- Systolic blood pressure < 90 mmHg for > 30 min
- Or catecholamines required to maintain pressure > 90 mmHg during systole
- Signs of pulmonary congestion
- Signs of impaired organ perfusion with at least one of the following criteria
 - Altered mental status
 - Cold, clammy skin and extremities
 - Oliguria with urine output < 30 ml/h
 - Lactate > 2.0 mmol/l

B. Septic shock

Septic shock is defined as described in the Third International Consensus Definitions for Sepsis and Septic Shock (Sepsis-3) (53) by the association of:

- Sepsis:
 - life-threatening organ dysfunction: acute change in total SOFA score ≥ 2 points consequent to the infection
 - caused by a dysregulated host response to infection.
- persisting hypotension requiring vasopressors to maintain mean arterial pressure ≥ 65 mm Hg
- serum lactate level > 2 mmol/L despite adequate volume resuscitation

8.2 Anticipated methods and timetable for measuring, collecting and analyzing the efficacy data

The parameters for assessing efficacy were collected according to the schedule in table paragraph 5.5.

9 SPECIFIC STUDY COMMITTEES

9.1 Steering Committee

The Steering Committee is composed of the principal investigator, the scientific director and members selected on the basis of outstanding expertise in the field and contribution to the study, one statistician and one sponsor (AP-HP) representative.

The Steering Committee is in charge of monitoring all activities towards the objective of the project in order to deliver as promised, in due time and in the budget. The Steering Committee shall thus:

- Control the execution of the project with regards to the project schedule and the description of work annexed to the protocol and to monitor corrective actions;
- Propose all significant modifications of the work plan or the protocol

The DRCI sponsor retains decision-making authority.

10 SAFETY ASSESSMENT - RISKS AND BURDEN ADDED BY THE STUDY

10.1 Description of Safety endpoints assessment parameters

There are no specific research protocol related-risks in ACORES-2 trial.

No invasive procedure is planned.

The only identified potential risks are related to withdrawal of RAS blockers which is evaluated by the primary safety endpoint of the trial.

10.2 Anticipated methods and timetable for measuring, collecting and analyzing the safety endpoints

The safety assessment shall be done by collecting all adverse events that occur during the research, all events shall be graded. Adverse events shall be collected according to the schedule in table of paragraph 5.5 of the protocol.

10.3 Recording and reporting adverse events

10.3.1 Definitions

According to Article R.1123-46 of the *Code de la Santé Publique* (French Public Health Code):

- **Adverse event**

Any untoward medical occurrence in a study participant, which does not necessarily have a causal relationship with the study or with the product subject to the study.

- **Adverse reaction**

An adverse event occurring in a study involving human participants when this event is related to the study or to the product being studied.

- **Adverse reaction to an investigational medicinal product**

Any untoward and unwanted reaction to an investigational medication regardless of the dose administered.

- **Serious adverse event or reaction**

"ACORES2" protocol, version 1-3 of 07/04/2020

Any adverse event or reaction that results in death, threatens the life of the participant enrolled in the study, requires hospitalization prolongs existing hospitalization, causes a severe or long-term disability or handicap, or results in a congenital abnormality or deformity, and in the case of a medication, regardless of the dose administered.

- **Unexpected adverse reaction in the experimental arm**

Any adverse reaction related to the discontinuation whose nature, severity, frequency or outcome is inconsistent with the standard safety information described in the summary of the product characteristics, or in the investigator's brochure if the product is not authorized.

According to Article R.1123-46 of the Code de la Santé Publique and the guidelines for sponsors of clinical trials (ANSM):

- **Emerging safety issue**

Any new information that may lead to a reassessment of the risk/benefit ratio of the trial or of the product under investigation, modifications in the investigational medicinal product use, the conduct of the clinical trial or the clinical trial documents, or a suspension, interruption or modification of the clinical trial or of similar trials.

For studies involving the first administration of a health product in healthy volunteers: any serious adverse reaction.

Examples:

- a) any clinically significant increase in the frequency of an expected serious adverse reaction;
- b) suspected unexpected serious adverse reactions in patients who have terminated their participation in the clinical trial which have been notified to by the investigator to the sponsor, as well as potential follow-up reports;
- c) any new fact relating to the conduct of the clinical trial or the development of the investigational medicinal product, if the new fact is likely to affect participant safety

Examples:

- a serious adverse event likely to be related to the trial's interventions and diagnostic procedures and which may impact the conduct of the clinical trial,
 - a significant risk for the trial participants such as a lack of efficacy of the investigational medicinal product used in the treatment of a life-threatening disease,
 - significant safety results from a recently completed study on animal subjects (such as a carcinogenicity study),
 - the premature termination, or temporary suspension, of a trial conducted with the same investigational medicinal product in another country, for safety reasons
 - an unexpected serious adverse reaction related to a non-investigational medicinal product required to conduct the trial, (e.g.: "challenge agents", rescue treatment)
- d) recommendations from the Data Safety Monitoring Board (DSMB), if they are relevant to the safety of the participants
 - e) any unexpected serious adverse reaction reported to the sponsor by another sponsor of a clinical trial carried out in a different country but relating to the same medication

